3.5.4 Guidelines for Diarrhea

Episodes of diarrhea have occurred in subjects receiving trametinib (see the Investigator Brochures [4] for more information). Other, frequent causes for diarrhea including concomitant medications (e.g., stool softeners, laxatives, antacids, etc.), infections by *C. difficile* or other pathogens, partial bowel obstruction, etc., should be clinically excluded.

Guidelines regarding management and dose reduction for diarrhea considered to be related to trametinib by the investigator are provided (see Table 11).

Table 11 Management and Dose Modification Guidelines for Diarrhea

CTCAE Grade	Adverse Event Management	Action and Dose Modification
Uncomplicated Diarrhea ^a Grade 1 or 2	
 • Diet: stop all lactose containing products; eat small meals, BRAT-diet (banana, rice, apples, toast) recommended • Hydration: 8-10 large glasses of clear liquids per day (e.g., Gatorade or broth) • Loperamide^c: initially 4 mg, followed by 2 mg every four hours or after every unformed stool; maximum 16 mg/day. Continue until diarrhea free for 12 hours • Diarrhea > 24h: loperamide 2 mg every two hours; maximum 16 mg/day. Consider adding oral antibiotics • Diarrhea > 48h: loperamide 2 mg every two hours; maximum 16 mg/day. Add budesonide or other second-line therapies (otretotide, or tincture of opium) and oral antibiotics 	
 • Continue trametinib • If diarrhea is grade 2 for > 48h, interrupt trametinib until diarrhea resolves to grade ≤ 1 • Restart trametinib at the same dose level • If treatment delay is > 14 days, discontinue trametinib.
Uncomplicated Diarrhea ^a Grade 3 or 4 Any Complicated Diarrhea ^b	
 • Clinical evaluation mandatory • Loperamide^c: initially 4 mg, followed by 2 mg every four hours or after every unformed stool; maximum 16 mg/day. Continue until diarrhea free for 12 hours • Oral antibiotics and second-line therapies if clinically indicated • Hydration: intravenous fluids if clinically indicated • Antibiotics (oral or intravenous) if clinically indicated • Intervention should be continued until the subject is diarrhea free for ≥ 24 hours • Intervention may require hospitalization for subjects at risk of life-threatening complications 	
 • Interrupt trametinib until diarrhea resolves to grade ≤1 • Restart with trametinib reduced by one dose level^d • If 3 dose reductions of study treatment are clinically indicated, permanently discontinue trametinib

Abbreviation: CTCAE = Common Terminology Criteria for Adverse Events

- **Uncomplicated diarrhea** defined by the absence of symptoms such as, cramping, nausea/vomiting ≥ grade 2, decreased performance status, pyrexia, sepsis, neutropenia grade ≥ 3, frank bleeding, and/or dehydration requiring intravenous fluid substitution
- **Complicated diarrhea** defined by the presence of symptoms such as, cramping, nausea/vomiting ≥ grade 2, decreased performance status, pyrexia, sepsis, neutropenia grade ≥ 3, frank bleeding, and/or dehydration requiring intravenous fluid substitution
- Loperamide should be made available prior to start of study treatment so loperamide administration can begin at the first signs of diarrhea
- Escalation of trametinib to previous dose level is allowed after consultation with the subprotocol Study Chair and in the absence of another episode of complicated or severe diarrhea in the 4 weeks subsequent to dose reduction.

Rev. 8/15

3.5.5 Trametinib Dose Modification for Toxicities Not Specified in Subsequent Sections

Rev. 8/15 **Table 12 Trametinib Treatment Modification for Clinically Significant Toxicities Deemed Related to Trametinib**

(This section is not for specific AEs such as hypertension, rash, ejection fraction changes, pneumonitis, diarrhea, liver chemistry, QTc prolongation, or visual changes. Refer to other sections for these specific AEs).		
CTCAE v4 Grade	Management Guideline	Dose Modification
Grade 1	Monitor as clinically indicated. Provide supportive care according to institutional standards.	Continue trametinib at current dose level.
Grade 2 (tolerable)		
 Interrupt treatment until resolution to grade 1 or baseline. Upon resolution, restart treatment at current dose level.
Grade 2 (intolerable) and Grade 3		
 Interrupt treatment until resolution to grade 1 or baseline. Upon resolution to baseline or grade 1, restart with one level of dose reduction. If the Grade 3 toxicity recurs, interrupt trametinib; When toxicity resolves to Grade 1 or baseline, restart trametinib reduced by another dose level.
Grade 4		
If event resolves to grade 1 or baseline discuss potential continuation of trametinib with the subprotocol Study Chair; if continuation of treatment agreed then restart trametinib at dose reduced by one dose level.
 
If event does not resolve, permanently discontinue trametinib.

Trametinib should be discontinued if treatment delay is ≥ 14 days due to toxicities. If the investigator concludes that continued trametinib will benefit a patient, the subprotocol Study Chair may be consulted for the possibility of resuming trametinib, provided that toxicities have resolved to baseline or grade 1.		

3.6 Supportive Care

All supportive measures consistent with optimal patient care will be given throughout the study. See adverse reaction sections, tables 9-12.

3.7 Duration of Agent-specific treatment

In the absence of treatment delays due to adverse event(s), treatment may continue until one of the following criteria applies:

- Extraordinary Medical Circumstances: If at any time the constraints of this protocol are detrimental to the patient's health, protocol treatment should be discontinued. In this event submit forms according to the instructions in the MATCH Forms Packet.
- Patient withdraws consent.
- Patient experiences unacceptable toxicity.
- Non-protocol therapies are administered.
- Disease progression

3.8 Duration of Follow-Up

Refer to the MATCH Master Protocol for specifics on the duration of follow-up.

Rev. 12/16 **4. Study Parameters**

Rev.2/16 4.1 Therapeutic Parameters for Trametinib Treatment

NOTE: In addition to the study parameters listed in the MATCH Master Protocol at Step 0, the below parameters must also be performed for patients on trametinib treatment.

NOTE: All assessments required prior to registration to treatment should be done ≤ 4 weeks prior to registration to Steps 1, 3, 5, 7, excluding the radiologic evaluation and electrocardiogram (ECG).

Test/Assessment	Prior to Registration to Treatment	Treatment		End of Treatment	Follow Up ^F
		Every Cycle, prior to treatment	Every 2 Cycles		
H&P, Weight, Vital signs ^A	X	X ^J			X
Performance status	X	X ^J			X
CBC w/diff, plts ^B	X	X ^J			X
Serum chemistry ^B	X	X ^J			X
Radiologic evaluation ^D	X		X ^D		X ^F
β-HCG ^C	X				
Toxicity Assessment ^G		X		X	X ^F
Pill Count/Diary ^H		X		X	
ECG ^{K,L}	X	X ^L			
Echocardiogram or Nuclear Study ^L	X	X ^L			
Eye Exam	X	X ^I			
Tumor biopsy and blood sample for MATCH Master Protocol ^E			X	X	

Rev. 8/15

Rev. 8/15

Rev. 3/17

A. History and physical, including vital signs and weight at the start of each cycle (up to 3 days before start of new cycle).

Rev.2/16

Rev. 8/15

B. Albumin, alkaline phosphatase, total bilirubin, bicarbonate, BUN, calcium, creatinine, glucose, phosphorus, potassium, SGOT[AST], SGPT[ALT], sodium, magnesium, and serum tumor markers (including LDH, PSA if appropriate). For eligibility purposes, participants with creatinine levels above institutional normal, Cockcroft-Gault will be used to calculate creatinine clearance. CBC w/diff, platelets and serum chemistries should be performed on cycle 1, day 1 (or up to 7 days prior), and at the start of each subsequent cycle (up to 3 days before start of new cycle). CBC with differential will be performed more frequently in patients with grade 4 neutropenia or thrombocytopenia until resolution to ≤ grade 3. CBC and serum chemistries are only required in follow-up until values return to pre-treatment levels or until progressive disease.

Rev.2/16

C. Blood pregnancy test (women of childbearing potential) required prior to beginning treatment.

- Rev.2/16 D. Disease measurements are repeated every 2 cycles for the first 26 cycles, and every 3 cycles thereafter until PD or start of another MATCH treatment step. The baseline evaluation should be performed as closely as possible to the beginning of treatment and never more than 6 weeks before registration to treatment step. For multiple myeloma patients, please refer to Section 6.4 of the MATCH Master Protocol for additional information on myeloma response criteria and the required disease assessments. Documentation (radiologic) must be provided for patients removed from study for progressive disease.
- Rev. 3/17, Add13 E. Additional blood specimens and/or biopsies are to be submitted from consenting patients per Section 9.3.2 of the MATCH Master Protocol. Submit at the following time points, as applicable:
- Blood specimens are to be submitted at the end of Cycle 2 (prior to start of Cycle 3 treatment). If patient progresses or treatment is discontinued prior to Cycle 3, collect the blood at that time instead. On-treatment kits for blood sample collections will be automatically shipped to sites upon registration to the treatment step.
 - Screening biopsies for additional aMOI assessments after registration to appropriate screening step, if applicable (Step 2 or Step 4).
 - At end of all MATCH study treatments, blood specimens and/or research biopsy after consent and registration to Step 8
- Please refer to Section 4 of the MATCH Master Protocol to determine whether the patient proceeds to the next screening step or to follow-up (with a potential end of treatment biopsy for research purposes on Step 8). Samples are to be submitted as outlined in Section 9 of the MATCH Master Protocol. To order Step 2/4 Screening or Step 8 kits, complete the EAY131 Collection and Shipping Kit Order Form (See Appendix XII of the MATCH Master Protocol) and fax to [contact].
- Rev.2/16 F. Every 3 months if patient is < 2 years from study entry, and every 6 months for year 3. Toxicity assessments and radiologic evaluations are not required to be done during Follow Up if progression has been previously reported; however if an adverse event occurs post treatment that meets the SAE reporting requirements, it still must be reported via CTEP-AERS, even if progression has occurred.
- G. Site personnel should evaluate for toxicity and discuss treatment compliance with the patient in order to ensure the medication is taken correctly; this evaluation may be conducted by telephone or in person. The Toxicity Assessment is not required prior to Cycle 1, but is required every subsequent cycle.
- H. The pill calendar will be collected at the end of every cycle. The Pill Count/Diary is not required prior to Cycle 1, but is required every subsequent cycle.
- I. As clinically indicated.
- J. For Cycle 1, if the following tests/assessments occurred within 7 days of Day 1, they do not need to be repeated at this timepoint: H&P, Weight, Vital Signs; Performance Status; CBC w/diff, plts; Serum chemistry; Concomitant Medications.
- K. Within 8 weeks of treatment assignment.
- Rev. 8/15 Rev. 2/16 L. Cardiac monitoring with ECG and ECHO/nuclear study (MUGA or First Pass) is needed at week 5, week 13, and every 12 weeks thereafter unless clinically indicated sooner. The same modality should be used at baseline and thereafter.

Rev.Add13

5. Drug Formulation and Procurement

This information has been prepared by the ECOG-ACRIN Pharmacy and Nursing Committees.

Availability

NO STARTER SUPPLIES MAY BE ORDERED. Subjects must be enrolled and assigned to the treatment subprotocol prior to submitting the clinical drug request to PMB.

Drug Ordering: NCI supplied agents may be requested by eligible participating Investigators (or their authorized designee) at each participating institution. Pharmaceutical Management Branch (PMB) policy requires that drug be shipped directly to the institution where the patient is to be treated. PMB does not permit the transfer of agents between institutions (unless prior approval from PMB is obtained – see general information) The CTEP-assigned protocol number must be used for ordering all CTEP-supplied investigational agents. The eligible participating investigators at each participating institution must be registered with CTEP, DCTD through an annual submission of FDA Form 1572 (Statement of Investigator), NCI Biosketch, Agent Shipment Form, and Financial Disclosure Form (FDF). If there are several participating investigators at one institution, CTEP-supplied investigational agents for the study should be ordered under the name of one lead investigator at that institution.

Submit agent requests through the PMB Online Agent Order Processing (OAOP) application (<https://ctepcore.nci.nih.gov/OAOP>). Access to OAOP requires the establishment of a CTEP Identity and Access Management (IAM) account (<https://ctepcore.nci.nih.gov/iam/>) and the maintenance of an “active” account status, a “current” password, and an active person registration status.

NCI Supplied Agent(s) – General Information

Questions about drug orders, transfers, returns, or accountability should be addressed to the PMB by calling [contact] Monday through Friday between 8:30 AM and 4:30 PM Eastern Time or email [contact] anytime.

Drug Returns: All undispensed drug supplies should be returned to the PMB. When it is necessary to return study drug (e.g., sealed bottles remaining when PMB sends a stock recovery letter), investigators should return the study drug to the PMB using the NCI Return Agent Form available on the NCI home page (<http://ctep.cancer.gov>).

Drug Accountability: The investigator, or a responsible party designated by the investigator, must maintain a careful record of the receipt, disposition, and return of agent received from the PMB using the NCI Investigational Agent Accountability Record Form for Oral Agents available on the NCI home page (<http://ctep.cancer.gov>). Maintain separate NCI Investigational Agent Accountability Records for each agent, strength, formulation and ordering investigator.

Investigator Brochure Availability: The current versions of the IBs for PMB-supplied agents will be accessible to site investigators and research staff through the PMB Online Agent Order Processing (OAOP) application. Access to OAOP requires the establishment of a CTEP Identity and Access Management (IAM) account and the maintenance of an “active” account status, a “current” password, and active person registration status. Questions about IB access may be directed to the PMB IB coordinator at [contact].

Rev. 3/17

Rev. 12/16	5.1	Trametinib (NSC 763093)
	5.1.1	Other Names MEKINIST™, GSK1120212, JTP-74057, JTP-78296, JTP-75303
	5.1.2	Classification MEK inhibitor
	5.1.3	Mode of Action Trametinib dimethyl sulfoxide is a reversible, highly selective, allosteric inhibitor of mitogen-activated extracellular signal regulated kinase 1 (MEK1) and MEK2. Tumor cells commonly have hyperactivated extracellular signal-related kinase (ERK) pathways in which MEK is a critical component. Trametinib dimethyl sulfoxide inhibits activation of MEK by RAF kinases and MEK kinases.
Rev. 8/15, 12/16	5.1.4	Storage and Stability Storage: Store tablets at 2°C -8°C in the original bottle. Do not repackage tablets or remove desiccant. Bottles should be protected from light and moisture. If a storage temperature excursion is identified, promptly return trametinib to 2°C -8°C and quarantine the supplies. Provide a detailed report of the excursion (including documentation of temperature monitoring and duration of the excursion) to [contact] for determination of suitability. Stability: Refer to the package label for expiration.
Rev. 12/16	5.1.5	Dose Specifics Trametinib will be given continuous dosing 2mg daily.
Rev. 8/15 Rev. 5/16	5.1.6	Preparation Novartis supplies and CTEP, NCI, DCTD distributes 0.5 mg and 2 mg (as free base) tablets. Each commercially-labeled bottle contains 30 tablets with a desiccant. The tablet core contains mannitol, microcrystalline cellulose, hypromellose, croscarmellose sodium, magnesium stearate (non-animal), colloidal silicon dioxide and sodium lauryl sulfate. 
• 0.5 mg tablets are yellow, modified oval, biconvex and film-coated with 'GS' debossed on one face and 'TFC' on the opposing face. Aqueous film coating consists of hypromellose, titanium dioxide, polyethylene glycol, iron oxide yellow.• 2 mg tablets are pink, round, biconvex and film-coated with 'GS' debossed on one face and 'HMJ' on the opposing face. Aqueous film coating consists of hypromellose, titanium dioxide, polyethylene glycol, polysorbate 80, iron oxide red.

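### Do footnotes D and F of Protocol Section 4.1 leave the scan interval undefined for patients who stop trametinib without progression?

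*Protocol*

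**What the plan says.** The schedule is the table in Protocol Section 4.1 with its footnotes. The note above the table says that "the below parameters must also be performed for patients on trametinib treatment".

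The row label is "Radiologic evaluation ^D". Within that row, the cell for every second cycle under Treatment carries D, and the Follow Up cell carries F. F also marks the heading of the Follow Up column.

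- **Footnote D:** measurements are "repeated every 2 cycles for the first 26 cycles, and every 3 cycles thereafter until PD or start of another MATCH treatment step". It also holds the baseline window, the myeloma reference and the requirement to document progression.
- **Footnote F:** "Every 3 months if patient is < 2 years from study entry, and every 6 months for year 3". It adds that "radiologic evaluations are not required to be done during Follow Up if progression has been previously reported".

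Protocol Section 3.8 says: "Refer to the MATCH Master Protocol for specifics on the duration of follow-up". Footnote E points to the Master Protocol "to determine whether the patient proceeds to the next screening step or to follow-up".

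**The concern.** Protocol Section 3.7 lets treatment end without progression, for example for unacceptable toxicity or withdrawal of consent. Take a patient who has stopped for toxicity, has not progressed and has started no other MATCH step. D's end rule names only progression and a new step, so on its wording alone D still applies. F applies because the patient is in Follow Up. No sentence in the subprotocol says which prevails.

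The row label adds some weight. Footnote B also sits on row labels, and it reaches into follow-up: "CBC and serum chemistries are only required in follow-up until values return to pre-treatment levels or until progressive disease". D might be thought to do the same.

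If sites read the table differently, the same kind of patient would be scanned every 8 weeks at one site and about every 13 at another. The recorded date of radiologic progression would then depend partly on the site's reading. With an accrual goal of 35, avoidable variation of that kind deserves a look.

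**Working it through.** **Intervals.** The inputs are the 28-day cycle (Protocol schema) and footnotes D and F.

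- D: 2 × 28 = 56 days = 8.0 weeks, up to 26 × 28 = 728 days = 104 weeks. After that, 3 × 28 = 84 days = 12 weeks.
- F: 3 × 365.25/12 = 91.3 days = 13.0 weeks before two years. In year 3, 6 × 365.25/12 = 182.6 days = 26.1 weeks.

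The two intervals do differ: 8 against about 13 weeks, a ratio of 91.3/56 = 1.63.

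**Size of the difference.** Mean lag from true progression to the next scan, for interval T:

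- Progression uniform within the interval: T/2, which is 4.0 weeks for T = 8 and 6.5 for T = 13. Difference 2.5 weeks.
- Exponential progression: T/(1 − exp(−λT)) − 1/λ, with λ = ln 2/median and 4.348 weeks per month. For a median of 4.8 months, 4.18 and 6.97 weeks, difference 2.79. For a median of 2.0 months, 4.42 and 7.60 weeks, difference 3.18.

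The two medians are the melanoma progression-free survival figures in Protocol Section 1.1.4. They were observed in other populations from the start of treatment. Using them as residual time after stopping is an assumption, made only to give a range.

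**One patient.** Assume that study entry and the first treatment day coincide, that trametinib stops at week 20, and that the last scan was at week 16. The next scan is at week 24 under D and at week 26 under F counted from study entry, the only date F names. These fall 8 and 10 weeks after the last scan. Further scans to week 104 without progression: under D at weeks 24, 32, …, 104, which is 11; under F at weeks 26, 39, …, 104, which is 7. Per year: 52/8 = 6.5 against 52/13 = 4, a difference of 2.5.

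**Which footnote governs?** Test each reading against the whole table.

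1. *D continues after trametinib stops.* Before progression D sets the interval. After reported progression F itself waives the scan. After another MATCH step starts, D ends and the patient is on a new treatment rather than in this table's Follow Up. The F in the Follow Up radiology cell would then set an interval for nobody.
2. *D applies on treatment and F in Follow Up.* Each footnote governs the column it marks. F's waiver after progression makes sense because it implies that unprogressed patients are scanned in Follow Up at F's interval.

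The Toxicity Assessment row is the closest parallel. Its label carries footnote G, which asks for an assessment at each cycle after the first and names no end at treatment stop. Its Follow Up cell carries F. Nobody would read G as requiring assessments every 28 days after the drug has stopped. The radiology row has the same layout.

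Footnote B differs. It reaches follow-up because it says so, and its Follow Up cells carry no competing footnote. D does not mention follow-up, and its Follow Up cell carries F.

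**The case for a change.** The best argument for a change is D's second end point. A patient who starts another MATCH treatment step has already left trametinib, so if D ended with the drug, that clause would have little to do. F also ties its two-year limit to study entry without saying from what date the 3-month visits are counted, so even a site that follows F has to choose. One sentence would remove both doubts.

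Part of this stands. D's end rule is loosely worded, and F's counting date is only implied. But every reading leaves something idle: the on-treatment reading makes one clause of D nearly redundant, while the other empties a marked cell of the table. The cell is the more specific instruction.

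The possible amendments also gain little. Extending D's 8-week interval to patients off drug would replace F's written interval and add about 2.5 scans per patient-year before week 104, with no endpoint effect shown. Lighter imaging off treatment is a legitimate trade-off, and nothing in the document suggests that it was unintended. Stating that D ends with treatment would only write out what the layout already conveys.

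**Conclusion.** No change to the plan follows. The 8-week and 13-week intervals belong to different columns, and the table, the cycle-based unit in D and the waiver in F together give one coherent rule: 8-weekly through cycle 26 while on trametinib, 3-monthly in Follow Up before two years. What remains is a loose end rule in D.

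If a site did read it the other way, the mean shift in detecting progression would be about 2.5 weeks under uniform timing and up to about 3.2 weeks under the assumed exponential range. It would affect only patients who are off drug, unprogressed and on no other MATCH step. Their number, and any effect on an endpoint, cannot be had from this document.

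This conclusion rests on the table layout as it appears in the available text. The Master Protocol was not available. It holds the duration of follow-up and the routing into it, and may state the imaging rule outright.

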5.1.7 Route of Administration

Oral. Take by mouth on an empty stomach, either 1 hour before or 2 hours after a meal. If a dose of trametinib is missed, the dose can be taken if it is more than 12 hours until the next scheduled dose.

